**8.2.3. Analysis of Other Endpoints**

**8.2.3.1. Demographic and Baseline Characteristics**

Statistics on demographic characteristics will be compiled for the PP efficacy, mITT efficacy, safety, mITT immunogenicity, and mITT colonization populations, except where noted.

Demographic and baseline characteristic analyses are summarized in Table 22.

**Table 22. Summary of Demographic and Baseline Characteristic Analyses**

Endpoint	Population	Statistical Method	Model/Covariates/Strata	Missing Data	Interpretation/Comments
Disposition	5 Populations	Descriptive	Vaccine group	N/A	Lines for enrolled, randomized, not vaccinated, vaccinated, surgery, no surgery, completed, and discontinued; discontinued further split by reason for discontinuation

**Table 22. Summary of Demographic and Baseline Characteristic Analyses**

Endpoint	Population	Statistical Method	Model/ Covariates/ Strata	Missing Data	Interpretation/Comments
Sex, race, racial designation, ethnicity, smoking status, age group, any alcohol use, colonization status, indication for surgery, age (in years), BMI, units of alcohol, Charlson Comorbidity Index score, Charlson mortality probability, ASA classification, vital signs, elapsed days from vaccination to index surgery	5 Populations	Descriptive	Vaccine group	N/A	
Medical history	Safety only	Descriptive	Vaccine group	N/A	
Physical examination	Safety only	Descriptive	Vaccine group	N/A	
Vaccine administration	mITT	Descriptive	Vaccine group	N/A	
Subjects with blood samples drawn for immunogenicity analysis	mITT	Descriptive	Vaccine group	N/A	

Abbreviations: ASA = American Society of Anesthesiologists; BMI = body mass index; e-diary = electronic diary; N/A = not applicable.

No subgroup analyses are proposed.

**8.2.3.2. Index Surgery and Hospitalization**

Vaccine groups will be compared in the safety, mITT efficacy, and PP efficacy populations.

The analyses will be performed for all subjects in the indicated populations, and then performed for the indicated subgroups:

- With and without postoperative BSI and/or deep incisional or organ/space SSI within 90 days
- With and without postoperative BSI and/or deep incisional or organ/space SSI within 180 days
- With and without postoperative SSI within 90 days
- With and without postoperative SSI within 180 days
- With and without postoperative SSI within 90 days

- With and without postoperative ISA disease within 180 days

These subgroup analyses will be limited to the mITT efficacy and PP efficacy populations. The tables with these analyses should include both levels of the indicated infection, eg, BSI yes/no, to facilitate identification of antagonistic or synergistic effects.

Index surgery and hospitalization analyses are summarized in Table 23.

**Table 23. Summary of Index Surgery and Hospitalization Analyses**

Endpoint	Population	Statistical Method	Model/Covariates/Strata	Missing Data	Interpretation/Comments
Variables where 1 level selected per subject, eg, Staphylococcus aureus carriage	Safety, mITT efficacy, PP efficacy	CMH	Site as stratification factor	N/A	
Variables where multiple levels may be selected per subject, eg, vertebrae fused	Safety, mITT efficacy, PP efficacy	Descriptive	Vaccine group	N/A	No statistical test because some subjects may report more than 1 level
Numeric, eg, glucose responses, duration of surgery, intraoperative blood loss	Safety, mITT efficacy, PP efficacy	van Elteren	Vaccine group, site as blocking factor	N/A	Glucose responses will be compiled by fasting and nonfasting status.
Variables where 1 level selected per subject, eg, S aureus carriage	mITT efficacy, PP efficacy	CMH	Site as stratification factor	N/A	Performed for each level of BSI yes/no, SSI yes/no, and ISA yes/no
Variables where multiple levels may be selected per subject, eg, vertebrae fused	mITT efficacy, PP efficacy	Descriptive	Vaccine group	N/A	Performed for each level of BSI yes/no, SSI yes/no, and ISA yes/no
Numeric, eg, glucose responses, duration of surgery, intraoperative blood loss	mITT efficacy, PP efficacy	van Elteren	Vaccine group, site as blocking factor	N/A	Performed for each level of BSI yes/no, SSI yes/no, and ISA yes/no.  Glucose responses will be compiled by fasting and nonfasting status.

Variables are classified as single level, multiple levels, and numeric in [Section 8.1.3.2](#).

Abbreviations: BSI = bloodstream infection; CMH = Cochran-Mantel-Haenszel;

ISA = invasive *Staphylococcus aureus*; N/A = not applicable; PP = per-protocol; SSI = surgical-site infection.

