#### **8.1.2.2. Methodology for Multiple-Organ Failure**

The denominators for organ systems that failed and subjects meeting MOF criteria will be all subjects in the safety population. Vaccine groups will be compared using the Fisher exact test, 2-sided, for each organ system. These p-values will include subjects with 2 or more failed systems, so they should be interpreted cautiously.

Subjects with MOF will be split into 2 categories: “associated with infection” (subdivided as “PDI” or “non-PDI [other infection]”) and “not associated with infection” (subdivided as “other [not an infection]” and “unknown”). The denominators will be all subjects in the safety population in order to obtain the absolute risk of subjects’ having MOF associated with infection. The Fisher exact test, 2-sided, will be used to compare vaccine groups in association with infection.

Subjects with MOF associated with infection will be further split into the categories “PDI” and “non-PDI (other infection).” The denominators will be all subjects in the safety

population. Vaccine groups will be compared in both the PDI and non-PDI subcategories with the Fisher exact test, 2-sided.

The subcategories PDI and non-PDI will each be further split into “microbiologically confirmed *S aureus* infection,” “microbiologically confirmed non-*S aureus*,” and “non-microbiologically confirmed infection.” “Non-microbiologically confirmed infection” will be further split into “negative” and “not done.” The denominators will be all subjects in the safety population. Vaccine groups will be compared in each level within each subcategory using the Fisher exact test, 2-sided.

Subjects with MOF not associated with infection will be further split into the categories “other” and “unknown.” The denominators will be all subjects in the safety population. Vaccine groups will be compared in the other and unknown subcategories with the Fisher exact test, 2-sided.

Site is not proposed as a stratification factor in any analyses because of the expected sparseness of MOFs.

Statistical analyses are summarized in [Section 8.2.2.2](#).

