### **8.1.3.3. Healthcare Utilization**

Healthcare utilization variables whose units are days (eg, number of days in an ICU) will be summarized by sample size, mean, standard deviation, median, minimum, and maximum. Vaccine groups will be compared using the van Elteren test, with site as the stratification variable.

Categorical variables (eg, interventional procedures, discharge disposition) will be summarized by frequency counts and proportion of subjects in each category. If a subject has more than 1 hospital admission leading to more than 1 response, only the earliest hospital admission will be included in the analysis. Vaccine groups will be compared using the CMH method, with site as the stratification variable.

The number of service visits will be summarized by sample size, mean, standard deviation, median, minimum, and maximum. Vaccine groups will be compared using the van Elteren test.

The number of rehabilitation/physical therapy visits will be summarized by sample size, mean, standard deviation, median, minimum, and maximum. Vaccine groups will be compared using the van Elteren test.

Zeroes will not be imputed to subjects without the indicated response, eg, number of days in a skilled nursing facility.

All healthcare variables will be reanalyzed, but limited to subjects from the mITT efficacy population who have at least 1 PDI. Subjects with more than 1 PDI may be included in more than 1 analysis. There will be 6 additional analyses, 1 for each type of PDI (BSI and/or deep incisional or organ/space SSI, SSI, or ISA disease) by 2 windows (1-90 and 1-180 days). Vaccine groups will be compared in numeric variables using the Mann-Whitney test and compared in categorical variables using the Fisher exact test. The statistical tests will not incorporate site because the number of PDIs per site will be small or zero.

Statistical analyses for healthcare utilization are summarized in [Section 8.2.3.3](#).

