### **8.2.1. Analyses for Efficacy**

All primary and secondary endpoints will be subjected to subgroup analysis, where SA4Ag and placebo will be compared at each level of the subgroup. Fifteen subgroups will be examined:

1. Race.
2. Age group.
3. Sex.
4. Ethnicity.
5. Smoking status.
6. Country.
7. CCI score.
8. Colonization at the time of surgery (performed for any *S aureus*).
9. Colonization at the time of surgery (performed for MRSA).
10. Colonization at the time of surgery (performed for MSSA).
11. Timing of the surgery after vaccination.

12. Presurgery decolonization (any/none).
13. Intrawound application of antibiotic (yes/no).
14. High-enrolling investigator sites (yes/no); the number of mITT subjects will be compiled by site. Sites with  $\geq 50$  mITT subjects will be considered high-enrolling sites.
15. High-attack rate investigator sites (yes/no); the number of mITT subjects with any PDI (BSI, deep incisional or organ/space SSI, superficial SSI, or ISA disease) will be compiled by site. The median of the nonzero values will be computed (only nonzero values will be included because multiple sites are expected to not have any PDI). Sites with the median or higher will be considered high-attack rate sites.

The subgroup analysis by timing of surgery after vaccination in the interval 1-14 days should be understood as an interval of 9-14 days in the PP efficacy population, because subjects with timing of 1-8 days after vaccination will be excluded from the PP efficacy population.

Subgroup analyses by site are not proposed because of the expected sparseness of cases.

Subgroup analyses will be performed in both the PP and mITT efficacy populations.

All analyses for 1 endpoint in 1 population, ie, all subjects plus every level of each subgroup, will be included in the same table.

Subgroup analyses will not be performed for postoperative ISA disease based on baseline *S aureus* colonization, because these are exploratory endpoints. Instead, baseline *S aureus* colonization will be included as a subgroup in the analyses of postoperative ISA disease.

Efficacy analyses are summarized in Table 14.

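### SAP Table 23 stratifies the arm comparisons among infected subjects by site, which SAP 8.1.3.3 rules out for infected subjects, and so weakens those tests

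*SAP*

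**What the plan says.** SAP 8.1.3.2 compares vaccine groups on surgical and hospitalization variables by CMH (categorical) and van Elteren (numeric), each with site as the stratum. It makes no exception for infected subjects. SAP 8.2.3.2 then asks for the same analyses in subjects with and without each infection endpoint, in the mITT and per-protocol efficacy populations. Table 23 marks these rows "Performed for each level of BSI yes/no, SSI yes/no, and ISA yes/no", with "Site as stratification factor" for CMH and "Vaccine group, site as blocking factor" for van Elteren.

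Elsewhere the SAP avoids site when events are few:

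- 8.1.3.3, healthcare utilization in subjects with a PDI: "The statistical tests will not incorporate site because the number of PDIs per site will be small or zero". The PDI rows of Table 24 use Mann-Whitney and Fisher exact.
- 8.1.2.2, multiple-organ failure: "Site is not proposed as a stratification factor in any analyses because of the expected sparseness of MOFs".
- 8.2.1, efficacy: "Subgroup analyses by site are not proposed because of the expected sparseness of cases". In defining high-attack-rate sites, the same section adds that "only nonzero values will be included because multiple sites are expected to not have any PDI".

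Separately, the six bullets in 8.2.3.2 list "With and without postoperative SSI within 90 days" twice and do not list ISA disease within 90 days.

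**The concern.** The SAP expects so few infections per site that it drops site from one set of tests on infected subjects, yet keeps it in another. The two sets overlap. Duration of hospitalization is a van Elteren variable in 8.1.3.2 and a Mann-Whitney variable in the PDI rows of Table 24, so for infected mITT subjects the SAP prescribes two tests and two p-values for one comparison.

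The Table 23 choice is the weaker one. Where infected subjects are thinly spread, many sites hold them in one arm only, and the stratified tests ignore those sites. What is at stake is the arm comparison among infected subjects for variables such as blood loss, duration of surgery, glucose and wound class. These are supportive analyses with no decision rule attached.

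**Working it through.** **Why a one-arm site drops out.** Take a site with *a* infected SA4Ag subjects, *b* infected placebo subjects and *t* = *a* + *b*.

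- CMH, binary variable: the site's variance is *a·b·m1·m2* / [*t*²(*t* − 1)], where *m1* and *m2* are the two response totals. If *a* or *b* is 0, the variance is 0 and observed minus expected is 0. The same happens if *m1* or *m2* is 0, so CMH needs both arms and both responses in the site.
- Van Elteren: the within-site rank sum has variance proportional to *a·b*, which is again 0 for a one-arm site.
- A site with one infected subject is always a one-arm site.

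**Inputs from the documents.** 51 confirmed *S aureus* SSI/BSI cases over both arms (SAP 8.1.3.5); 62 case subjects including other *S aureus* infections (SAP Table 13); interim analysis at 24 per-protocol cases; 1:1 allocation. The plan gives no figure for infected subjects per site, so there is none to reproduce.

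**Assumptions.** Number of sites *S* = 50 to 150. Site sizes are either equal or skewed (gamma, shape 1). At VE 0% each infected subject is equally likely to be in either arm.

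**Closed form, equal sites, VE 0%.** An infected subject counts if at least one of the other *n* − 1 is in the same site and the other arm:

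share = 1 − (1 − 0.5/*S*)^(*n* − 1)

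- *n* = 51, *S* = 50: 1 − 0.99^50 = 0.395
- *n* = 51, *S* = 100: 1 − 0.995^50 = 0.222
- *n* = 51, *S* = 150: 1 − (1 − 1/300)^50 = 0.154
- *n* = 150, *S* = 50: 1 − 0.99^149 = 0.776

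**Simulation, 51 infected, VE 0%** (1500 runs per setting):

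| Sites | Both arms, equal | Both arms, skewed | CMH-usable, equal | CMH-usable, skewed |
|---|---|---|---|---|
| 50 | 40% | 56% | 26% | 43% |
| 75 | 28% | 44% | 17% | 32% |
| 100 | 22% | 36% | 13% | 25% |
| 150 | 16% | 27% | 9% | 17% |

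The CMH columns are for a binary variable with 50% prevalence. The equal-site column agrees with the closed form. Measured as the sum over sites of *ab*/*t*, divided by the unstratified *ab*/*n*, the information kept falls from 0.38 to 0.16 (equal) or from 0.51 to 0.26 (skewed) across 50 to 150 sites.

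**Sensitivity.**

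- Over 24 to 62 infected subjects, 50 to 150 sites and VE 0% or 70%, the both-arms share is 5-46% (equal) or 10-61% (skewed).
- With many infected subjects per site, exp(−0.5λ) = 0.5 gives λ = 1.386 infected subjects per site as the point where the share is 50%. For 51 cases that is 51/1.386 = about 37 equal sites.
- With 24 infected subjects and 150 equal sites, the share is 1 − (1 − 1/300)^23 = 0.074, or 24 × 0.074 = about 1.8 subjects. In such a setting some datasets would have no usable site, and the statistic could not be calculated.

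**The case against.** The strongest reply is that the size of the loss is not known. A reader might infer that most sites have at most one infected subject and that the tests throw away most of the data. The documents do not establish either statement. They speak only of small or zero counts and of sparseness, and give no site count. With 50 strongly skewed sites, van Elteren would keep 56% of 51 infected subjects, or 61% of 62. This part of the reply stands, and the size must be read as conditional.

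The infected groups may also be larger than 51. The BSI and SSI bullets in 8.2.3.2 do not name *S aureus*, and SAP 6.1.3 has separate any-pathogen endpoints. With 150 infected subjects at 50 equal sites about 78% would be kept. This stands as well, although ISA disease is *S aureus* by definition and the conflict with 8.1.3.3 remains on either reading.

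A reader might further infer that the search for antagonistic or synergistic effects cannot work. That goes too far. The sentence in 8.2.3.2 concerns showing both infection levels in one table. The counts, proportions, means and medians in that table use every infected subject. Only the p-values lose information, and a within-level p-value would not test interaction in any case.

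SAP 8.1.4 allows sparse subgroup analyses to be skipped, but it introduces that rule for efficacy and selected immunogenicity subgroups. It does not clearly reach Table 23, and skipping a test does not settle which test is specified.

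Finally, one might say that the 90-day ISA table is lost. The three-endpoint by two-window grid in 8.1.3.3 and 8.2.3.3 makes the intended sixth bullet plain, so this is a typographical slip.

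**Conclusion.** The inconsistency is certain and rests on the text alone: 8.1.3.2 and Table 23 stratify infected-subject comparisons by site, while 8.1.3.3 and Table 24 decline to do so for a reason that applies equally to Table 23. That one-arm sites contribute nothing is algebra.

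The size is conditional on assumed site numbers and site-size skew. For 50 to 150 sites, 51 *S aureus*-infected subjects and VE 0%, roughly 16-40% (equal) or 27-56% (skewed) of infected subjects would be in a site with both arms, and fewer would be usable for CMH. Fewer sites or an any-pathogen definition would reduce the loss. The infected-level p-values would lose much of their power, and some may be incalculable.

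The point is minor. The descriptive summaries, the all-subject and uninfected comparisons, and the unstratified binomial analysis of the primary endpoint are untouched.

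**What to change.** - In SAP 8.1.3.2 and Table 23 together, specify unstratified Fisher exact (categorical) and Mann-Whitney (numeric) tests for the infected level, as 8.1.3.3 already does. Keep site stratification for the all-subject and uninfected levels. Changing Table 23 alone would leave it in conflict with 8.1.3.2.
- In 8.2.3.2, state whether the BSI and SSI bullets mean *S aureus* infection only or any pathogen.
- In 8.2.3.2, replace the second 90-day SSI bullet with ISA disease within 90 days, to match the grid in 8.1.3.3 and 8.2.3.3.

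The cost is a few lines of SAP wording and a changed test option in the programs. No new data are needed.

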### 8.2.3.3. Healthcare Utilization

All analyses will be performed in the mITT efficacy population. No subgroup analyses are proposed.

Healthcare variables will be reanalyzed, but limited to subjects adjudicated to have 1 of 3 endpoints (BSI and/or organ/space or deep incisional SSI, SSI, or ISA disease) crossed with 2 windows (1-90 and 1-180 days after surgery).

Healthcare utilization analyses are summarized in Table 24.

**Table 24. Summary of Healthcare Utilization Analyses**

Endpoint	Population	Statistical Method	Stratification	Missing Data	Interpretation/Comments
Numeric healthcare utilization: 
 
• duration of hospitalization
 
• number of readmissions related to complications of index surgery
 
• number of days in the ICU
 
• total hospitalizations from index surgery and any readmissions
 
• total days in ICU from index surgery and any readmissions
 
• number of rehabilitation/physical therapy visits as an outpatient
 
• number of service visits
 
• number of inpatient days in rehabilitation or nursing facility
 
	mITT	van Elteren	Site	N/A	Impact of vaccination on subsequent healthcare use

**Table 24. Summary of Healthcare Utilization Analyses**

Endpoint	Population	Statistical Method	Stratification	Missing Data	Interpretation/Comments
Categorical healthcare utilization: 
 
• location prior to hospital admission
 
• ongoing hospitalization, yes/no
 
• discharge disposition
 
• proportion of readmissions to hospital
 
• proportion of readmissions related to complications of index surgery
 
• additional surgery
 
• proportion in an ICU in readmission
 
• proportion discharge after readmission
 
	mITT	CMH	Site	N/A	Impact of vaccination on subsequent healthcare use
Numeric healthcare utilization: 
 
• duration of hospitalization
 
• number of readmissions related to complications of index surgery
 
• number of days in the ICU
 
• total hospitalization from index surgery and any readmissions
 
• total days in ICU from index surgery and any readmissions
 
• number of service visits
 
• number of inpatient days in rehabilitation or nursing facility
 
	Any subject with PDI	Mann-Whitney	N/A	N/A	Impact of vaccination on subsequent healthcare use, limited to subjects with PDIs  Performed for PDIs in 1-90 and in 1-180 days

**Table 24. Summary of Healthcare Utilization Analyses**

Endpoint	Population	Statistical Method	Stratification	Missing Data	Interpretation/Comments
Categorical healthcare utilization: 
 
• location prior to hospital admission
 
• ongoing hospitalization, yes/no
 
• discharge disposition
 
• proportion of readmissions to hospital
 
• proportion of readmissions related to complications of index surgery
 
• additional surgery
 
• proportion in an ICU in readmission
 
• proportion discharge after readmission
 
	Any subject with PDI	Fisher exact	N/A	N/A	Impact of vaccination on subsequent healthcare use, limited to subjects with PDIs  Performed for PDIs in 1-90 and in 1-180 days

Abbreviations: CMH = Cochran-Mantel-Haenszel; ICU = intensive care unit; N/A = not applicable; PDI = protocol-defined infection.

**8.2.3.4. Colonization with *Staphylococcus aureus***

All analyses will be performed using the mITT colonization population.

The proportions of subjects with positive swabs will be plotted against time point. The time points' labels on the figures will be "Day of Vaccination," "Day of Surgery," "Day of Discharge," "Day 42," "Day 90," and "Day 180." The values for the time points will be -15, 1, 2, 42, 80, and 180. The legend will identify anatomical site (nasal/oropharyngeal/combined). Plots will be created for "any *S aureus*," MSSA, and MRSA.

Subgroup analyses will be performed on colonization, carriage status, acquisition, and clearance. The subgroups will be age group, sex, baseline colonization status, and primary endpoint (case or noncase). The subgroup analysis of the primary endpoint will be limited to scheduled visits within 90 days, as per definition of the primary endpoint.

A further subgroup will be defined by subjects having any decolonization measures or preadmission antimicrobial agent(s) before surgery (response = yes/no). These analyses will be performed only for "any *S aureus*."

The analysis of matching isolates from microbiologically confirmed cases will be performed separately for nose and throat for each of the efficacy endpoints (BSI and/or deep incisional or organ/space SSI within 90 days, BSI and/or deep incisional or organ/space SSI within 180 days, SSI within 90 days, SSI within 180 days, ISA disease within 90 days, and ISA disease within 180 days), but limited to subjects in the mITT colonization population. If there may be more than 48 cases for the primary endpoint, ie, with BSI and/or deep incisional or organ/space SSI, these extra cases will be included in this analysis.

Colonization analyses and their statistical tests are summarized in Table 25.

**Table 25. Summary of Colonization Analyses**

Endpoint	Population	Statistical Method	Model/Covariates/Strata	Missing Data	Interpretation/Comments
Proportions of subjects colonized with Staphylococcus aureus on each visit	mITT colonization	CMH	Site as stratification variable	N/A	Explore colonization patterns between vaccine groups longitudinally Perform for any S aureus , MRSA, and MSSA
Carriage status (persistent, intermittent, etc)	mITT colonization	CMH	Site as stratification variable	N/A	Explore effect of vaccination of carriage duration Perform for any S aureus , MRSA, and MSSA
Acquisition	mITT colonization	CMH	Site as stratification variable	N/A	Explore effect of vaccination on acquiring S aureus Perform for any S aureus , MRSA, and MSSA
Clearance	mITT colonization	CMH	Site as stratification variable	N/A	Explore effect of vaccination on clearing S aureus . Perform for any S aureus , MRSA, and MSSA
Colonization at unscheduled visits	mITT colonization	Fisher exact		N/A	Colonization in suspected BSI/SSI cases Perform for any S aureus , MRSA, and MSSA
Association between strain colonizing subject and strain recovered from infection	mITT colonization	Fisher exact	Nose and throat separately	N/A	Repeat for all efficacy endpoints
Subgroup analysis on proportions colonized	mITT colonization	Logistic regression	Vaccine group, subgroup, and interaction	N/A	Examine interaction of subgroup and vaccine. Perform for any S aureus . Nose and throat separately
Infection-colonization	mITT colonization	Fisher exact	N/A	N/A	Are subjects self-infecting?

Abbreviations: BSI = bloodstream infection; CMH = Cochran-Mantel-Haenszel; MSSA = methicillin-sensitive *Staphylococcus aureus*; MRSA = methicillin-resistant *Staphylococcus aureus*; MSSA = methicillin-sensitive *Staphylococcus aureus*; N/A = not applicable; PDI = protocol-defined infection; SSI = surgical-site infection.

